19.1 General Considerations

Statistical analysis is the responsibility of the CTRU Trial Statistician under the supervision of the Supervising Statistician, except for the health economic analysis which is the responsibility of the health economic TMG member. A full statistical analysis plan will be written before any analyses are undertaken and in accordance with CTRU standard operating procedures.

19.2 Analysis populations

Analyses will be conducted on the intention to treat (ITT) basis where participants will be included according to which treatment they were randomised to receive, apart from the safety/tolerability endpoint which will be based on the safety population. The safety population will consist of all patients who take at least one dose of any trial treatment; analyses based on the safety population will summarise participants according to treatment received. All hypothesis tests will be two-sided and will use a 5% significance level.

Sensitivity analyses may be performed for each endpoint, for example to take into account differing assumptions about missing data if there is a significant number of missing data, and will be detailed in the full statistical analysis plan.

19.3 Frequency of analysis

A DMEC will be set up to independently review data on safety and recruitment. Interim reports will be presented to the DMEC in strict confidence, on at least yearly intervals. This committee, in light of the interim data and of any advice or evidence they wish to request, will advise the TSC if there is proof beyond reasonable doubt that one treatment is better. No formal interim analyses are planned hence no statistical testing will take place until final analysis.

We do not propose interim futility or early stopping (for superiority) analyses. Given the relatively short recruitment and follow-up periods in this trial, and the absence of a plausible reason to believe that outcomes would be worse in the EPA arm, we are highly unlikely to have observed sufficient events to stop for futility at 2½ years because of limited overall follow-up. Similarly, the relative paucity of events expected halfway through the four-year interventional period (i.e. at the end of recruitment) means that there would have to be a huge implausible difference in PFS in favour of EPA in order to stop for superiority.

The final analysis will take place after the last patient recruited has been followed up for 24 months or the number of events required has been reached, whichever occurs first.

19.4 Primary endpoint analysis

The primary endpoint is progression free survival (PFS) (see section 17 for definition).

PFS will be analysed using the 95% confidence interval of the hazard ratio; the 95% confidence interval of the difference in median PFS will also be presented to aid interpretation. Kaplan-Meier survival curves will be calculated for PFS. Patients without a PFS event at the time of analysis will be censored at the time they were last known to be alive and progression-free. Differences in PFS between the treatment groups will be compared using multivariate modelling (for example, an extended Cox model if appropriate) to adjust for the minimisation factors of 'downsizing' chemotherapy, extrahepatic CRC metastases, randomising centre, and time between randomisation and surgery and also regular aspirin use during follow-up which will be included as a time dependent covariate. A sensitivity analysis will also be conducted to examine the effects of other potential effect modifiers in addition to the minimisation factors. The primary analysis will be the multivariate analysis which adjusts for the minimisation factors and regular aspirin use during follow-up. Treatment HRs and corresponding 95% confidence intervals will be obtained from the multivariate models.

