Although EPA (or placebo) treatment was limited to the pre-operative period, overall survival (OS) and disease-free survival (DFS) were specified as exploratory end-points on the basis that oral dosing with EPA before liver surgery would provide tissue EPA exposure in the immediate peri-operative period with prolonged bioavailability in the post-operative period due to the slow tissue 'washout' kinetics of EPA¹². Survival analysis demonstrated that the median DFS in the EPA-FFA group was 22.6 months compared with 14.7 months in the placebo group. Any DFS benefit was explained by a reduction in CRC recurrence from 12 months after surgery onwards²⁷. A Cox multivariate analysis revealed that EPA treatment was associated with improved DFS (hazard ratio [HR] 0.35 [95% confidence interval 0.15-0.79]). EPA use also conferred OS benefit with 7 CRC-related deaths in 41 evaluable CRCLM patients who received EPA-FFA compared with 14 deaths in 42 placebo group patients (HR 0.40 [95% confidence interval 0.16-1.0])²⁷.

The two previous adequately powered RCTs of perioperative chemotherapy in patients undergoing CRCLM resection, including the most recent New EPOC trial, both used PFS as the primary endpoint²⁸⁻²⁹. These trials are not directly comparable to the EMT study due to differences in the study populations related to trial exclusion criteria and historical differences in hepatobiliary surgical practice²⁷. However, the median PFS in these trials²⁸⁻²⁹ and smaller preceding studies³⁰ is slightly longer (approximately 21 months *versus* 15 months) than the median PFS in the placebo arm of the EMT study²⁷. Two-year OS in the EMT study was 71.5% compared with 78-79% OS in the control arm of the two most recent trials²⁸⁻²⁹, perhaps related to not having preoperative chemotherapy as an exclusion criterion, and wider inclusion criteria in the latter trials.

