13.7 Visits 7-9: Treatment Assessments and Data Collection

Participants should have a trial visit at 30, 36 and 42 months (+/- 2 weeks) after the date of CRCLM surgery. The following assessments will be carried out at each visit:

- Clinical evaluation to assess for disease progression and new primary cancer, as per local standard practice.
- Toxicity assessment: collection of any adverse events which may have occurred since the last trial visit.
- Details of hospital resource activity (e.g. hospital inpatient stays, outpatient clinics attending, accident and emergency attendances).
- Participant self-reported assessments: the EQ-5D, EORTC QLQ-C30 and QLQ-LMC21 Quality of Life questionnaires and a health economics questionnaire will be administered to the participant in a Participant Questionnaire Visit 3-10 Pack. Questionnaires should be completed by participants at the time of clinical assessment, but before discussion of the outcome of any medical assessments or blood tests wherever possible.
- Participants should be provided with a Participant Diary Booklet to record information over the next visit period. The information collected in the booklet will be the information to be collected in the health economics questionnaire and details on compliance and adverse events. The booklet is intended to act as a reminder to the participant and must not be handed in to clinic or returned to the CTRU.
- Weight in kilograms (in light indoor clothing and without shoes).
- CT scan of thorax, abdomen and pelvis at visit 8 only: CT scans are carried out on an annual basis after 2 years post CRCLM surgery.
- Treatment compliance: the participant will be asked if they have missed any treatment doses since the last trial visit and for what reason.
- Details of concomitant medications including over-the-counter O3FA supplements since the last trial visit. Participants should be reminded that over-the-counter O3FA supplements are prohibited.
- One box of IMP will be dispensed.

- The IMP dispensed at the previous visit should be checked regarding the expiry date and the participant should be advised to use the IMP box currently in use before opening the IMP box dispensed at the most recent visit.
- See Biospecimen Collection protocol if participant is already in this sub-study. A sample collection pack may need handing /posting to the participant at visit 7.

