18.1 Sample size and planned recruitment rates

18.1.1 Sample size

At study outset it was specified that a sample size of 448 participants (giving 247 events) would be required to detect a HR of 0.7 for PFS in favour of EPA (the treatment arm) with a power of 80% at the 5% (2-sided) level of significance. This assumes the control arm has a median PFS of 21 months and the treatment arm has a median PFS of 30 months. It also assumed a 24 month recruitment period and a minimum 24 months follow up, and allowed for 10% dropout.

In advance of protocol version 9.0, in light of the slower than expected recruitment rate and based on the recommendation of the independent DMEC and TSC, a minimum sample size of 388 was specified. This minimum sample size takes into account a revised 67 month

recruitment period and the minimum 24 month follow-up. It was determined by considering the effect of the extended study duration and the opportunity to observe the required events in fewer patients observed for greater time. This revised minimum sample size also allows for the observed higher rate of 15% dropout related to the COVID-19 pandemic and other protocol compliance issues. All other design parameters remain unchanged, including the given number of events required to trigger analysis (247 events).

The HR for PFS in the Phase II EMT study²⁷ was 0.694, but the EPA arm, by chance, recruited a higher proportion of patients with poor prognostic features, and a multivariate analysis including these factors actually yielded a HR of 0.35 (95% confidence interval: 0.15-0.79) lending credence to the assumed more conservative HR of 0.7 chosen for this larger phase III study, given that the magnitude of benefit observed in phase II studies is often greater than that observed in the phase III counterpart.

The EMT study tested EPA-FFA 2g daily²⁷. Although the EMT2 study will evaluate IPE 4 g daily, we assume similar efficacy of EPA given as IPE, compared with EPA-FFA, for the purposes of the trial power calculation.

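### The supportive difference in median PFS (section 19.4) depends on where the medians fall between scheduled CT scans; a PFS difference just after the 24-month scan would be steadier

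*Protocol*

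**What the plan says.** **Analysis (protocol 19.4).** The primary analysis is a multivariate model giving an adjusted HR with its 95% CI. Kaplan-Meier curves are planned, and "the 95% confidence interval of the difference in median PFS will also be presented to aid interpretation".

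**Dating of events (13.12, 17.1).** PFS runs from randomisation. Progression takes the date of the scan or assessment that identifies it. Deaths keep their own date. Clear clinical progression without imaging counts at the clinical date and is expected to be uncommon.

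**Scan calendar (13.5 to 13.8, Appendix A).** CT is scheduled at 6, 12, 18, 24, 36 and 48 months after surgery, with none at 30 or 42 months. Section 13.7 says "CT scans are carried out on an annual basis after 2 years post CRCLM surgery". Clinical review continues at 30 and 42 months. Participants followed remotely are scanned under local surveillance (13.5).

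**Design (18.1.1).** The stated sample size "would be required to detect a HR of 0.7 for PFS in favour of EPA", "with a power of 80% at the 5% (2-sided) level of significance". On the medians: "This assumes the control arm has a median PFS of 21 months and the treatment arm has a median PFS of 30 months".

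No section states what share of PFS events will be dated away from a scheduled scan.

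**The concern.** When most events carry a scan date, the Kaplan-Meier curve is nearly flat between scans and drops at each one. The time at which it crosses 0.5 is then close to a scan time, whatever the underlying median is within that interval. The difference between two such medians reflects the spacing of the scans as well as the treatment effect.

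The design values are badly placed for this. The 21-month median lies shortly before the 24-month scan, and the 30-month median lies in the 12-month gap between the 24- and 36-month scans. Section 19.4 chooses this statistic to help readers interpret the HR, and it is the only absolute measure reported there with a confidence interval. At stake is how the size of the benefit is described, not whether a benefit is declared.

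**Working it through.** **1. The plan's own figures.** The Schoenfeld formula with HR 0.7, 5% two-sided and 80% power gives 4 × (1.960 + 0.842)² / (ln 0.7)² = 246.8, so 247 events, as stated.

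With exponential medians of 21 and 30, hazard λ = ln 2 / median, uniform accrual over R months and minimum follow-up F = 24, the event probability in an arm is 1 − [exp(−λF) − exp(−λ(R+F))] / (λR).
- R = 24: mean probability 0.623; 247 / 0.623 ≈ 397; with 10% dropout, 397 / 0.90 gives 442 (stated 448).
- R = 67: mean probability 0.763; 247 / 0.763 ≈ 324; with 15% dropout, 324 / 0.85 gives 382 (stated 388).

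Exponential medians of 21 and 30 are therefore a fair reading of the design.

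**2. Where the curves cross one half.** S(t) = 0.5^(t/median), timed from surgery for simplicity.

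| Arm | 18 months | 24 months | 36 months |
|---|---|---|---|
| Control (21) | 0.552 | 0.453 | 0.305 |
| IPE (30) | 0.660 | 0.574 | 0.435 |

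If every event is scan-dated, control crosses 0.5 at the 24-month scan and IPE at the 36-month scan. The difference is about 12 months against a true 30 − 21 = 9.

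**3. Events dated off-scan.** Let q be the share of events that keep their true date. Just before a scan, observed survival is (1 − q) × S(previous scan) + q × S(this scan). The crossing stays at the scan while this exceeds 0.5:
- control: 0.552 − q × (0.552 − 0.453) = 0.5 gives q = 0.052 / 0.099 ≈ 0.525
- IPE: 0.574 − q × (0.574 − 0.435) = 0.5 gives q = 0.074 / 0.139 ≈ 0.532

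The effect therefore persists up to about half of events off-scan. The protocol does not give q, so it was varied.

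**4. Large-sample simulation.** Times run from randomisation, surgery is 1 to 6 weeks later (an assumption within the limit of under 6 weeks in 13.4), and scans are ±2 weeks. With q = 0 the observed medians are 24.7 and 36.8, a difference of 12.1 months.

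| q | 0.15 | 0.30 | 0.40 | 0.50 | 0.60 | 0.75 |
|---|---|---|---|---|---|---|
| Displayed difference (months) | 12.1 | 12.2 | 12.2 | 12.5 | 11.4 | 10.1 |

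At q = 1 it returns to about 9.

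**5. Other true values.** The treatment median is the control median divided by the HR.

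| Control median, HR | True difference | Displayed difference |
|---|---|---|
| 14.7, 0.7 | 6.3 | 6.1 (q = 0 to 0.3) |
| 17, 0.7 | 7.3 | 6.3 to 6.4 (q = 0 to 0.3) |
| 18, 0.7 | 7.7 | about 17 (q = 0); about 7.5 (q = 0.5) |
| 25, 0.7 | 10.7 | about 1.5 (q = 0) |
| 21, 0.85 | 3.7 | 1.0 to 1.1 (q = 0 to 0.3) |

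The control-25 row shows how fragile the statistic is. With a mean surgery lag of 3.5 weeks (about 0.8 months), the 24-month scan falls near month 24.8, where control survival is 0.5^(24.8/25) = 0.503. That is just above one half, so the control median jumps to the 36-month scan, beside the IPE median.

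**6. One trial.** With 194 per arm and q = 0, the 5th to 95th percentiles of the displayed difference run from under 1 month to about 18 months. About 72% of trials fall between 10.5 and 13.5 at q = 0, and about a third at q = 0.5.

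**7. A steadier summary.** The latest scheduled 24-month scan falls 24 months + 6 weeks + 2 weeks ≈ 25.8 months after randomisation. At month 26 the true difference is 0.5^(26/30) − 0.5^(26/21) = 0.548 − 0.424, or about 12.4 points. If all events are scan-dated, what is seen is survival at about month 24.8: 0.564 − 0.441 = 12.3 points. In the simulations this difference stayed within about 0.2 points of the truth. The difference in restricted mean survival time (RMST) to 50 months was 4.7 to 5.0 against a true 5.2, so slightly conservative.

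**8. The HR.** The same grid applies to both arms, and the Cox HR fitted to grid-dated data stays at about 0.70.

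**The case against.** **The statistic is only supportive.** This stands. The adjusted HR is the primary result. A reader might infer that the trial's main result is biased; it is not, and the event target and the test are untouched.

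**The bias favours the drug.** A reader might infer this from the 12-versus-9 result. The documents do not support it: the table in step 5 shows differences that are nearly right, too large and too small, depending on where the medians fall.

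**The 21 months may already include detection delay.** Section 6.2.1 describes PFS in earlier trials as "slightly longer (approximately 21 months", which is a reported median. The protocol does not give those trials' scan schedules, so this cannot be settled. If it is a scan-detected figure, 9 months is not the right reference value, and both the size and the direction of the error change.

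**The gap from 24 to 36 months is not the sole cause.** This also stands. Six-monthly CT throughout would show under 7 months against a true 9. The cause is dating on a grid, and nothing here argues for a different scan calendar.

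**Kaplan-Meier curves already show absolute PFS, and the SAP may add more.** This is partly right. The curves let a reader take off a 24-month value, but 19.4 attaches an interval only to the median difference. The point concerns a statistic that the protocol itself selects, not one it leaves out.

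**Sampling error exceeds a 3-month shift.** True, but that is a further reason not to rely on this statistic.

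**Conclusion.** The point holds as a modest, inexpensive improvement. Under the design's own exponential medians, taken as true rather than scan-detected, and with at most about half of events dated off-scan, the expected display is about 12 months instead of 9. It moves towards 9 as the off-scan share rises. Section 13.12 expects progression without imaging to be uncommon, which suggests a low share, but deaths and unscheduled detections add to it and no figure is given.

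The result is conditional on those assumptions. It does not show that the published median difference will be overstated by a third: other medians or HRs give other errors, and one trial may land far from the expected value. What can be said generally is that, on this scan grid, the median difference is a poor guide to the absolute effect. The PFS difference just after the 24-month scan is a good one, from the same data.

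**What to change.** In section 19.4, and correspondingly in the SAP, before unblinding:

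- Add, as the main absolute summary, the difference in PFS proportion with 95% CI at a fixed time just after the scheduled 24-month scan, for example month 26 from randomisation. For two-stage resections, section 13.2 times the first post-operative CT from the second operation, so check whether a few 24-month scans fall later than month 26 when fixing the time.
- Optionally add an RMST difference, noting that it is slightly conservative on this grid.
- If the median difference is kept, estimate it with an interval-censored model, placing the event between the last clear assessment and the assessment showing progression. Otherwise label it as limited by the scan schedule.

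The cost is a change of wording and a little more analysis work. No new visits or data are needed, and the HR analysis and event target stay as they are. The downside is that a familiar summary loses prominence.

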10.4.2 Treatment Allocation

Participants will be randomised on a 1:1 basis to receive either IPE 4 g daily or placebo and will be allocated a trial number and a unique kit-code to identify which box of capsules (active [IPE] or placebo) will be dispensed. The participant's randomisation allocation will not be disclosed in order to maintain the blinding of the trial.

A computer-generated minimisation programme that incorporates a random element will be used to ensure that treatment groups are well balanced for the following participant characteristics, details of which will be required for randomisation:

- 'Downsizing' chemotherapy prior to liver resection* (yes or no)
- Known extrahepatic CRC metastases with curative treatment planned (yes or no)
- Current regular (intention to use daily) aspirin use:

- yes to current regular aspirin use
- no to current regular aspirin use
- Add-aspirin trial participant still taking IMP (placebo or aspirin, double-blind trial so treatment allocation not required to be known at EMT2 randomisation)
- Randomising Centre
- Time between randomisation date and date of planned liver resection surgery (<2 weeks or ≥2 weeks)

*For definition see Section 9.4

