12.2.3. Known Toxicities

As this is a blinded trial, adverse events should be assessed for a causal relationship assuming the participant has been receiving active IPE.

The active IMP (IPE 4 g per day; Vazkepa®) is licensed for use in the UK for reduction of the risk of cardiovascular events in adults, who have elevated triglyceride levels despite statin treatment and have established cardiovascular disease, or diabetes and at least one other cardiovascular risk factor. The safety profile and adverse reactions associated with IPE 4 g per day, which are described in the Summary of Product Characteristics (SmPC) for IPE approved by the MHRA, are based largely on the REDUCE-IT trial of 8179 individuals with a median age of 64 years, male sex 71% and white race 90%⁵⁴. These characteristics are similar to the proposed EMT2 trial population, who have CRC and are likely to have fewer cardiovascular risk factors. Therefore, the SmPC will be used as the Reference Safety Information (RSI) for IPE (see [link](#)).

The most frequently reported adverse reactions associated with IPE are bleeding (11.8%), peripheral oedema (7.8%), atrial fibrillation (5.8%), constipation (5.4%), musculoskeletal pain (4.3%), gout (4.3%) and rash (3.0%). A list of adverse reactions and frequencies is available in the IPE SmPC.

Bleeding occurred in 11.8% of subjects receiving IPE in the REDUCE-IT trial compared with 9.9% in subjects receiving placebo. Serious bleeding events were reported more frequently in subjects receiving IPE than in those receiving placebo when administered in combination with concomitant antithrombotic medication (3.4% vs. 2.6%), but occurred at the same rate (0.2%) in subjects not taking concomitant anticoagulant/antiplatelet medication. The bleeding events most frequently observed with IPE were gastrointestinal bleeding (3.1%), contusion (2.5%), haematuria (1.9%), and epistaxis (1.5%).

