13.10 Extended follow up phase

The participant's clinical records should be reviewed at 60 and 72 months after the date of CRCLM surgery/randomisation for participants who have consented to extended follow-up to collect any evidence of disease progression or a new primary cancer.

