19.5 Secondary endpoint analysis

Kaplan-Meier survival curves will be calculated for Overall Survival (OS). Participants without an OS event at the time of analysis will be censored at the time they were last known to be alive. Differences in OS between the treatment groups will be compared using multivariate

modelling (for example, an extended Cox model if appropriate) to adjust for the minimisation factors and regular aspirin use during follow-up, which will be included as a time dependent covariate, and subsequent analyses will be conducted to examine the effects of other potential effect modifiers in addition to the minimisation factors. Treatment HRs and corresponding 95% confidence intervals will be obtained from the multivariate models.

Safety analyses will summarise the AE, AR, SAE, SAR and SUSAR rates per participant, by treatment received and overall. Suspected relationship to IPE will be presented along with other causality, outcome and event duration.

QoL will be measured using the general EQ-5D and cancer specific EORTC QLQ-C30 and QLQ-LMC21 questionnaires. These will be analysed using random effects (multi-level) models to account for the hierarchical nature of repeated measures data and the models will include adjustments for baseline QoL, the minimisation factors and regular aspirin use during follow-up, which will be included as a time dependent covariate, with subsequent sensitivity analyses to adjust for any other potential effect modifiers in addition to the minimisation factors. The nature of any missing data will be investigated and if it is suspected that data are not missing at random alternative analyses will be carried out to allow for the nature of the missing data.

The number and timing of new primary cancers will be summarised descriptively by treatment group.

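### The primary PFS model adjusts for aspirin use after randomisation, and its list of factors leaves out baseline aspirin; baseline values should be used instead (should fix; likely effect on the HR small)

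*Protocol*

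**What the plan says.** Section 10.4.2 lists five minimisation factors: downsizing chemotherapy, extrahepatic metastases, current regular aspirin use, centre, and planned time to surgery. Aspirin has three levels: yes, no, and "Add-aspirin trial participant still taking IMP (placebo or aspirin, double-blind trial so treatment allocation not required to be known at EMT2 randomisation".

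Section 19.4 names the other four factors for the PFS model and adds regular aspirin use during follow-up as a time-dependent covariate. It then fixes the status of that model: "The primary analysis will be the multivariate analysis which adjusts for the minimisation factors and regular aspirin use during follow-up". The planned sensitivity analysis adds further effect modifiers; it does not remove post-randomisation aspirin.

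Section 19.5 specifies the OS model "to adjust for the minimisation factors and regular aspirin use during follow-up, which will be included as a time dependent covariate". The QoL models in 19.5 and the lean body mass and weight models in 19.7 carry the same covariate. Section 19.2 promises analysis by intention to treat.

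Aspirin may be used freely on trial (12.2.2). Concomitant medication is collected at calls and visits up to Visit 10, at about 48 months after surgery (13.3 to 13.8, Appendix A). The later record reviews are "to collect any evidence of disease progression or a new primary cancer" (13.10; 13.11 is similar), and the Trial Summary adds overall survival.

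**The concern.** An intention-to-treat HR compares groups formed by randomisation. If the model conditions on something that happens afterwards and that treatment can alter, the HR no longer describes the effect of being assigned IPE. It then leaves out whatever part of the effect runs through aspirin, and it can pick up bias if the same patient characteristics drive both stopping aspirin and progression.

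The protocol supplies material for both links:

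- **Treatment to aspirin.** "Bleeding occurred in 11.8% of subjects receiving IPE in the REDUCE-IT trial compared with 9.9% in subjects receiving placebo" (12.2.3). The same section gives atrial fibrillation or flutter as 5.8% against 4.5%. Either event could prompt a change in antiplatelet use, and blinding does not prevent this because the events themselves differ by arm.
- **Aspirin to outcome.** Section 6.2.3 says that aspirin may have activity against liver metastases, possibly additive with EPA.

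Measurement is a second problem. Add-Aspirin participants are blinded to aspirin or placebo, and patients may also join that trial after surgery (9.5). After Visit 10 the covariate has no planned data source. At stake is the one confirmatory analysis, together with the treatment comparisons for OS, QoL, lean body mass and weight.

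**Working it through.** **1. The plan's own figure.** Section 18.1.1 gives the number of events "required to detect a HR of 0.7 for PFS in favour of EPA", "with a power of 80% at the 5% (2-sided) level of significance", as 247. By Schoenfeld's formula, d = 4(1.960 + 0.842)² / (ln 0.7)² = 246.8, so 247. The figure is reproduced, and the choice of aspirin covariate does not enter it.

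**2. Share of PFS events after medication collection ends.** Inputs from 18.1.1: "This assumes the control arm has a median PFS of 21 months and the treatment arm has a median PFS of 30 months"; N = 388, 67 months' recruitment, 24 months' minimum follow-up, 15% dropout. Added assumptions: exponential PFS, uniform accrual, dropout as a simple 15% loss, and a cut at 48 months from randomisation.

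- Monthly hazards: ln 2/21 = 0.0330 and ln 2/30 = 0.0231. Potential follow-up is uniform from 24 to 91 months.
- Event probability over full follow-up: 0.818 (control) and 0.708 (IPE), mean 0.763. Events: 388 × 0.85 × 0.763 = 251.6.
- Event probability with follow-up cut at 48 months: 0.756 and 0.630, mean 0.693. Events: 228.7.
- Difference: 251.6 − 228.7 = 22.9 events, or 22.9/251.6 = 9.1%.
- Participants with potential follow-up beyond 48 months: (91 − 48)/67 = 64%.

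The 9% is an upper figure. Extended follow-up needs separate consent (13.8), Visit 10 is timed from surgery and so falls later than 48 months from randomisation, and the analysis may be triggered at 247 events (19.3).

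**3. Effect on the treatment HR.** The protocol gives no aspirin prevalence, switching rate or aspirin HR, so these are assumptions: 25% users at baseline, aspirin HR 0.8 or 0.6, and a simulated treatment HR of 0.7. A Cox model with baseline aspirin and one with time-dependent aspirin were fitted to the same 6,000 simulated patients, twice per scenario.

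| Scenario | Baseline → time-dependent, run 1 | Run 2 | Change |
|---|---|---|---|
| Same stopping rate in both arms (0.005/month), aspirin HR 0.8 | 0.687 → 0.687 | 0.707 → 0.708 | none material |
| Stopping 0.015 (IPE) vs 0.005, aspirin HR 0.8 | 0.694 → 0.688 | 0.760 → 0.753 | about 1% lower |
| Stopping 0.05 (IPE) vs 0.005, aspirin HR 0.6 | 0.714 → 0.674 | 0.693 → 0.653 | about 6% lower |
| As above, with frailty | 0.798 → 0.758 | 0.815 → 0.772 | about 5% lower |
| IPE starts aspirin at 0.005/month, aspirin HR 0.8, with frailty | 0.727 → 0.735 | 0.715 → 0.720 | about 1% higher |

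Single HRs carry simulation error; the paired differences are the informative part.

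**4. Scale.** With 247 events the SE of the log HR is about 2/√247 = 0.127, so a 95% interval around 0.70 runs from 0.55 to 0.90. A 1% shift is about 0.07 SE. The largest shift in the table, ln(0.653/0.693) = −0.059, is about 0.47 SE.

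**The case against.** **Baseline aspirin may already be in the model.** A reader might infer that the plan drops it. The list in 19.4 suggests so, but the summary sentence there and the wording in 19.5 can be read as all five factors plus follow-up aspirin. Omission is therefore not established. The ambiguity stands, and the post-randomisation term remains under either reading.

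**Nothing shows that IPE changes aspirin use.** This is correct. The protocol reports more bleeding and atrial fibrillation on IPE, not more stopping of aspirin. The excess is (11.8 − 9.9) + (5.8 − 4.5) = 3.2 percentage points over a median of 4.9 years. Suppose every excess event ended aspirin use, against an assumed background of 1% per month. The proportion still on aspirin after 58.8 months falls from exp(−0.588) = 0.555 to 0.523, a rate ratio of −ln(0.523)/0.588, about 1.10. In a separate simulation at that ratio the two HRs differed by only 0.002 to 0.004. The larger shifts above need much stronger switching.

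**The two models answer different questions.** Much of the gap is one of estimand: the effect of assignment including changes in aspirin use, or the effect with aspirin held fixed. That is fair, but intention to treat calls for the former.

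**Observation is better than it looks.** Over-the-counter drugs are recorded (12.2.2), Add-Aspirin participation goes on the Follow-Up CRF (9.5), and about 91% of events fall inside the collection window. The baseline factor has the same blinded third level. These points reduce the problem, but allocation in Add-Aspirin stays unknown, and 19.4 gives such participants no value for regular use.

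**Aspirin is of scientific interest.** It is, and the aspirin subgroup analysis in 19.6 and a sensitivity analysis can serve that interest.

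**Conclusion.** The concern holds as a matter of specification, at should-fix level. The confirmatory PFS model conditions on a post-randomisation variable that treatment could plausibly affect and that is only partly observed, and no PFS model with baseline covariates only is stated.

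The numerical consequence is probably small: nil without differential switching, about 1% of the HR with moderate switching, and 5-6% with strong switching and a strong aspirin effect. All of this rests on assumed aspirin inputs.

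Two stronger conclusions are tempting and not supported. One is that the analysis flatters IPE: that follows only if IPE users stop aspirin more often and aspirin is protective, and the shift reverses if IPE leads to more aspirin starts. The other is that the randomised comparison is broken: the documents show a possible route to bias, not one in operation. The case for change is that neither size nor direction can be known in advance, while baseline adjustment avoids this source of bias.

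**What to change.** In 19.4, state that the primary Cox model contains treatment and all five minimisation factors as recorded at randomisation, including baseline aspirin status at its three levels (yes, no, Add-Aspirin participant). Move the model with time-dependent aspirin to a sensitivity analysis. There, say how Add-Aspirin participants and time after Visit 10 are coded.

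Make the same change to the treatment comparisons for OS and QoL in 19.5 and for lean body mass and weight in 19.7. The models in 19.7 relating red-cell EPA or muscle mass to outcome are association analyses and need not follow.

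The cost is wording in three sections and matching text in the SAP, best settled before unblinding. No new data are needed, because baseline aspirin is already captured at randomisation. The 247 events, N of 448 (revised minimum 388) and 80% power are unchanged.
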